	Statistical comparison will be made between the change from baseline at each time point between the Groups 1 and 3 (extensive metabolizers) versus Groups 2 and 4 (poor metabolizers) for each treatment (AT -10 and Clopidogrel).
	The incidence of signs of bleeding from the abbreviated physical examination and the incidence of abnormal liver function tests (ALT, AST, total bilirubin, and alkaline phosphatase) will be tabulated for the treatment groups. The incidence of these events will not be formally tested and the comparison will be observational only. The observational comparisons will be made between the AT -10 and Clopidogrel in the extensive metabolizers and poor metabolizers.
	Pharmacokinetics:
	Pharmacokinetic parameters (AUCt, AUCinf, Cmax, tmax, t¼, kel, Cl/F, Vd/F) will be estimated following noncompartmental analysis of plasma concentration time-course data for Clopidogrel, AT -10 (2-oxo-clopidogrel), and MP-H4. PK parameters at steady-state will be estimated for Clopidogrel, AT-10 (2-oxo- clopidogrel), and MP-H4. Statistical comparison of the single-dose and multiple-dose PK parameters of peak (Cmax) and total (AUCt, AUCinf) exposure for the AT-10 and MP-H4 will be made between the AT-10 and Clopidogrel dose groups; between and within metabolizer groups.
	Although this is not a bioequivalence study following PK comparison will be made:
	• PK comparisons will be made for AT -10 and MP-H4 from AT -10 treatment in extensive metabolizers versus Clopidogrel treatment in extensive metabolizers
	• PK comparisons will be made for AT -10 and MP-H4 from AT -10 treatment in poor metabolizers versus Clopidogrel treatment in poor metabolizers
	• PK comparisons will be made for AT -10 and MP-H4 from AT -10 treatments in extensive metabolizers versus AT -10 treatments in poor metabolizers.
	Other PK comparison will be made if deemed appropriate
Safety Assessment	Tolerability and safety will also be assessed.
	Safety assessments will include screening, pre-dose and post-dose vital signs, ECGs, clinical laboratory testing (hematology, blood chemistry, and urinalysis), documentation of AEs and clinical examinations. Coagulation parameters (PT and PTT) will also be assessed at screening, at housing during each period, at 8 hrs post-dose on each dosing day and at exit or early termination.

Page 17 of 74

Ipca Laboratories Ltd Version 1.0 (Amendment 3.0)

[figure not shown]

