6 STUDY OBJECTIVES AND RATIONALE

6.1 STUDY OBJECTIVES

Primary:

- To determine the safety and tolerability of AT -10 compared to Clopidogrel administered orally to humans.
- To compare effect of AT -10 (loading and maintenance doses) Vs approved doses of Clopidogrel (loading and maintenance doses) on platelet aggregation in poor and extensive metabolizers.
- To confirm the AT -10 loading dose (PD equivalent dose to the Clopidogrel 300 mg) and the AT -10 maintenance dose (PD equivalent to the Clopidogrel 75 mg) given as a loading dose followed by 5 days of maintenance dose

Secondary:

• To determine the single and multiple dose pharmacokinetics (PK) of Clopidogrel, AT -10, and active metabolite MP-H4.

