14.3 PHARMACOKINETIC PARAMETERS AND ANALYSIS

Pharmacokinetic parameters (AUCt, AUCinf, Cmax, tmax, t½, kel, Cl/F, Vd/F) will be estimated following noncompartmental analysis of plasma concentration time-course data for Clopidogrel, AT -10 (2-oxo-clopidogrel), and MP-H4. PK parameters at steady-state will be estimated for Clopidogrel, AT - 10(2-oxo-clopidogrel), and MP-H4. Statistical comparison of the single-dose and multiple-dose PK parameters of peak (Cmax) and total (AUCt, AUCinf) exposure for the AT-10 and MP-H4 will be made between the AT-10 and Clopidogrel dose groups; between and within metabolizer groups. Additionally, geometric means will be calculated for AUCt, AUCinf, and Cmax. Analyses of variance (ANOVA) will be performed on the ln-transformed PK parameters AUCt, AUCinf, and Cmax. Each ANOVA will include calculation of least-squares means (LSMs), the differences between adjusted means, and the standard error associated with these differences. Ratios of means will be calculated using the LSM for Lntransformed AUCt, AUCinf, and Cmax. Although this is not a bioequivalence study, statistical comparison of the PK of AT-10 and MP-H4 between the AT-10 and Clopidogrel dose groups will be performed.

CONFIDENTIAL

Page 62 of 74

Although this is not a bioequivalence study following PK comparison will be made:

- PK comparisons will be made for AT -10 and MP-H4 from AT -10 treatment in extensive metabolizers versus Clopidogrel treatment in extensive metabolizers
- PK comparisons will be made for AT -10 and MP-H4 from AT -10 treatment in poor metabolizers versus Clopidogrel treatment in poor metabolizers
- PK comparisons will be made for AT -10 and MP-H4 from AT -10 treatments in extensive metabolizers versus AT -10 treatments in poor metabolizers.

The 90% confidence interval of the relative mean (geometric least square mean) of AT -10 and MP-H4 from AT -10 treatment versus Clopidogrel treatment for Ln-transformed Pharmacokinetic parameters Cmax, AUCt, AUC(0-inf) will be computed. Other PK comparison will be made if deemed appropriate.

C _{max}	Maximum measured plasma concentration over the time span specified		
T _{max}	Time of the maximum measured plasma concentration. If the maximum		
	value occurs at more than one time point, T _{max} is defined as the first time		
	point with this value		
AUC _{0-t}	Area under the concentration-time curve from time zero to the last sample		

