14.4 PHARMACODYNAMIC EFFECT ANALYSIS

ADP induced platelet aggregation will be assessed for change from baseline in each treatment group at each time point assessed on each dosing day (0.5, 2 and 6 hours post dose) and 24 hrs post dosing of last dosing day in each period. The change over time for each parameter will also be assessed.

Platelet inhibition will be calculated as per below formula.

Platelet Inhibition = $(1 - \text{Residual Impedance} / \text{Baseline Impedance}) \times 100$

The results will be reported as either residual platelet aggregation, measured as maximal amplitude of impedance (ohms), or platelet inhibition. The data from treatment groups 1 and 3 will be combined in the CONFIDENTIAL Page 63 of 74

analysis and similarly for treatment group 2 and 4 will be combined in the analysis. Statistical comparison will be made between the change from baseline at each time point between the treatment groups 1 and 3 (extensive metabolizers) versus treatment groups 2 and 4 (poor metabolizers) for each treatment (AT -10 and Clopidogrel). If applicable, as clinical phase of study will be conducted in group of volunteers not more than 18, volunteer group effect will also be analyzed statistically.

The incidence of signs of bleeding from the abbreviated physical examination and the incidence of abnormal liver function tests (ALT, AST, total bilirubin, and alkaline phosphatase) will be tabulated for the treatment groups. The incidence of these events will not be formally tested and the comparison will be observational only. The observational comparisons will be made between the AT -10 and Clopidogrel in the extensive metabolizers and poor metabolizers.

Additionally, the relationship between the PK of MP-H4 and pharmacodynamic measurements will be addressed using population PK-PD analysis.

CONFIDENTIAL

Page 64 of 74

Ipca Laboratories Ltd Version 1.0 (Amendment 3.0)

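### The protocol's named statistical comparison for platelet aggregation is extensive versus poor metabolizers within each drug; it names no AT-10 versus clopidogrel comparison, which primary objectives 2 and 3 ask for

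*Protocol*

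**What the plan says.** Protocol section 6.1 lists three primary objectives. The second compares AT-10 "Vs approved doses of Clopidogrel (loading and maintenance doses) on platelet aggregation in poor and extensive metabolizers". The third is "To confirm the AT -10 loading dose (PD equivalent dose to the Clopidogrel 300 mg"), with a matching statement for the maintenance dose and clopidogrel 75 mg.

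Section 14.4 sets out the pharmacodynamic (PD) analysis. It begins: "ADP induced platelet aggregation will be assessed for change from baseline in each treatment group", at each post-dose time, together with change over time. Groups 1 and 3 are then pooled, as are groups 2 and 4, and the statistical comparison of change from baseline is "between the treatment groups 1 and 3 (extensive metabolizers) versus treatment groups 2 and 4 (poor metabolizers) for each treatment (AT -10 and Clopidogrel"). The synopsis says the same: "between the Groups 1 and 3 (extensive metabolizers) versus Groups 2 and 4 (poor metabolizers) for each treatment (AT -10 and Clopidogrel"). Section 14.4 also mentions a volunteer-group (batch) effect if applicable, and a population PK-PD analysis relating the active metabolite MP-H4 to the PD measurements.

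Comparisons between the drugs are written out elsewhere. For pharmacokinetics, a secondary objective, section 14.3 states: "PK comparisons will be made for AT -10 and MP-H4 from AT -10 treatment in extensive metabolizers versus Clopidogrel treatment in extensive metabolizers". It has a parallel line for poor metabolizers and adds: "The 90% confidence interval of the relative mean (geometric least square mean) of AT -10 and MP-H4 from AT -10 treatment versus Clopidogrel treatment". For bleeding signs and liver tests, section 14.4 states: "The observational comparisons will be made between the AT -10 and Clopidogrel in the extensive metabolizers and poor metabolizers".

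**The concern.** Objectives 2 and 3 concern the difference between drugs within the same kind of person. The contrast called a statistical comparison concerns the difference between kinds of people on the same drug. The two do not match, although the crossover gives every subject both drugs and so supports the first directly.

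At stake is what the study can state about its dose. A small gap between extensive and poor metabolizers on AT-10 would be reported as the statistical PD result. The same gap could accompany a 40/10 mg regimen that inhibits platelets as much as clopidogrel 300/75 mg, much more, or less. Excess matters as well as deficit, since the protocol's background section names bleeding as a risk of thienopyridines.

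**Working it through.** The protocol gives no PD power, margin or variability to reproduce. Section 8 says that the sample size does not rest on a PD calculation. The check therefore has two parts.

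**1. What the named contrasts can show.** Write the four mean values of platelet inhibition as AE and AP (AT-10, extensive and poor) and CE and CP (clopidogrel, extensive and poor).

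- Named in 14.4 and the synopsis: AE - AP, and CE - CP.
- Needed for objective 2: AE - CE, and AP - CP. Objective 3 needs one or both.

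Adding a constant k to both AT-10 means leaves AE - AP unchanged but moves AE - CE and AP - CP by k. A rank check on the contrast vectors agrees: the drug difference lies outside the span of the two named contrasts in extensive metabolizers, in poor metabolizers and pooled. Only (AE - AP) - (CE - CP), the drug-by-class interaction, can be recovered.

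Illustrative means in % inhibition (assumed, not from the protocol):

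| AE / AP / CE / CP | AE - AP | CE - CP | AE - CE | AP - CP |
|---|---|---|---|---|
| 50 / 45 / 50 / 30 | 5 | 20 | 0 | +15 |
| 80 / 75 / 50 / 30 | 5 | 20 | +30 | +45 |
| 40 / 35 / 50 / 30 | 5 | 20 | -10 | +5 |

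The interaction is 5 - 20 = -15 in all three rows. The named contrasts are identical; the answers to the primary objectives are not.

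**2. Whether the existing design can give the missing contrast.** Inputs from section 7.1: 20 subjects per class, 1:1 to sequence, each receiving both drugs, withdrawals not replaced. Assumed: within-subject SD (SDw) of 10, 15 or 20 points.

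Half-width of the 90% CI for AT-10 minus clopidogrel in one class = t(0.95, n - 2) × SDw × √(2/n).

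- n = 20: 1.734 × 0.316 = 0.548, so 5.5, 8.2 or 11.0 points.
- n = 16 (an assumed four withdrawals in a class): factor 0.623, so 6.2, 9.3 or 12.5 points.
- Difference for which the 90% CI excludes zero with 80% power, n = 20: 8.2, 12.3 or 16.4 points.
- A true difference of 30 points at SDw 20, n = 20: power 0.998.

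For comparison with the contrast now named, assume a total SD of 15 points and a within-subject correlation of 0.5. Then SDw = 15 × √0.5 = 10.6, and the within-subject drug comparison has a half-width of 5.8 points. The extensive-poor comparison (20 versus 20, 38 degrees of freedom) has 8.0 points. Over total SDs of 10 to 20 and correlations of 0.3 to 0.7 the ranges are 3.0 to 9.2 and 5.3 to 10.7 points. On these assumptions the missing contrast is the more precise of the two.

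**The case against.** The strongest reply is that the protocol does not say its metabolizer comparison is the only one. Objective 2 already states the drug comparison, the crossover is built to deliver it, and a statistical analysis plan that specified it would follow the protocol. That stands to the extent that nothing is excluded. It does not remove the mismatch. The protocol is not silent on the PD contrast: it names one in two places, and that one does not answer two primary objectives. The drug contrast is spelled out for secondary pharmacokinetics and for bleeding signs and liver tests, but not for platelet aggregation.

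A second reply is that change from baseline per treatment group is a required output, so drug-specific levels will be reported in both classes, and the three scenarios above would look different in those tables. This also stands. A reader might infer from the mismatch that the trial cannot answer objectives 2 and 3, or will yield no information on the drug difference. The documents do not support that: the data will exist and the levels can be set side by side. A side-by-side reading, however, gives no estimate of the difference with an interval and does not use the pairing within subjects. The population PK-PD analysis, with the between-drug comparison of MP-H4 in 14.3, is an indirect, model-based route and does not replace a direct contrast.

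Third, section 8 describes the PD data as proof of concept, so formal equivalence testing may seem too much for 40 subjects. That weighs against demanding power, not against estimating what the objective names; objective 3 is itself worded as confirming equivalence. Finally, extensive versus poor within each drug is a sensible test of the rationale that AT-10 depends less on CYP2C19. It belongs in the plan, in addition.

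**Conclusion.** The point holds in this form: section 14.4 and the synopsis name a statistical PD comparison that does not deliver the between-drug comparison of objective 2 or the confirmation of PD equivalence of objective 3, and no AT-10 versus clopidogrel comparison of platelet aggregation is named. That the two named contrasts carry no information on the level of the drug difference is algebra and needs no assumption. The scenario differences of 0, +30 and -10 points only illustrate it. The half-widths of 5.5 to 11.0 points rest on an assumed within-subject SD of 10 to 20 points; they show that the remedy is feasible and do not measure the defect. The fault lies in the specified analysis and not in the design, so it should be corrected before analysis but puts no data at risk.

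**What to change.** In section 14.4 and the synopsis:

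- Name a within-subject (crossover) AT-10 minus clopidogrel comparison of platelet inhibition with a 90% CI, separately in extensive and in poor metabolizers, for loading (Day 1) and maintenance (Day 6). Both classes serve objective 2.
- State that PD equivalence of 40/10 mg to 300/75 mg (objective 3) is judged two-sidedly from this comparison, so that excess inhibition counts against it as well as deficit. State the class or classes to which it applies. Extensive metabolizers are the natural choice, because section 6.2 takes the doses from a study in that class. The margin can be set in the statistical analysis plan.
- Keep extensive versus poor within each drug as a further comparison.

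The cost is text only. Every subject already receives both drugs, and PD samples are already taken on all six dosing days of both periods, so no subject, dose or sample is added. The downside is that objective 3 can then fail, or be inconclusive if within-subject variability is high: at an SD of 20 points the 90% CI would extend about 11 points either side with 20 subjects, and 12.5 with 16.

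### The one statistical contrast the protocol writes for platelet aggregation is genotype against genotype within each drug, so the two primary AT-10 versus clopidogrel objectives have no matching inferential analysis

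*Protocol*

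**What the plan says.** Section 6.1 lists three primary objectives. The first is safety and tolerability. The other two are drug against drug on pharmacodynamics:

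- Objective 2, which covers both metabolizer types: "To compare effect of AT -10 (loading and maintenance doses) Vs approved doses of Clopidogrel (loading and maintenance doses) on platelet aggregation".
- Objective 3: "To confirm the AT -10 loading dose (PD equivalent dose to the Clopidogrel 300 mg"), and likewise the AT-10 "maintenance dose (PD equivalent to the Clopidogrel 75 mg) given as a loading dose followed by 5 days of maintenance dose".

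Section 14.4 combines groups 1 and 3 and groups 2 and 4. It then names the statistical comparison of change from baseline at each time point: "groups 1 and 3 (extensive metabolizers) versus treatment groups 2 and 4 (poor metabolizers) for each treatment (AT -10 and Clopidogrel". The synopsis has the same contrast: "Groups 1 and 3 (extensive metabolizers) versus Groups 2 and 4 (poor metabolizers) for each treatment (AT -10 and Clopidogrel".

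The only place in 14.4 where AT-10 is set against clopidogrel concerns bleeding signs and abnormal liver tests, and there "The incidence of these events will not be formally tested and the comparison will be observational only".

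**The concern.** The written contrast runs across genotypes while holding the drug fixed. Objectives 2 and 3 need a contrast across drugs while holding the genotype fixed. A team that carried out 14.4 exactly as worded would have inferential results on how much CYP2C19 status matters for each drug, but none on how the two drugs differ. A statement that the doses are equivalent would then rest on reading two sets of descriptive results side by side or, worse, on a non-significant result.

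The design makes the gap harder to accept. The crossover is there so that each subject provides a randomised, within-subject comparison of AT-10 with clopidogrel. The contrast that 14.4 names is between different subjects, on a characteristic that cannot be randomised.

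**Working it through.** The protocol gives no PD power calculation, SD or margin, so there is no stated PD figure to reproduce. Section 8 says openly that the sample size does not rest on a calculation of PD effect. The only stated figure that can be checked is 4 groups × 10 = 40 subjects, or 20 per metabolizer type. The main check is textual.

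**Step 1. Each analysis item in 14.4, and whether it compares the drugs on aggregation.**

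| Item in 14.4 | What it contrasts | AT-10 vs clopidogrel on aggregation? |
|---|---|---|
| "ADP induced platelet aggregation will be assessed for change from baseline in each treatment group at each time point assessed on each dosing day" | Each time point with baseline, within a treatment group | No |
| Change over time | Time, within a treatment group | No |
| The named statistical comparison | Extensive vs poor metabolizers, within each drug | No |
| "volunteer group effect will also be analyzed statistically" | Housing batches | No |
| Bleeding signs and liver tests | AT-10 vs clopidogrel, untested | No; not aggregation |
| Population PK-PD analysis | MP-H4 exposure against response | No |

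**Step 2. Count the contrasts.** Post-dose PD times are 0.5, 2 and 6 hours on six dosing days, plus 24 hours after the last dose: 6 × 3 + 1 = 19. With two drugs, 19 × 2 = 38 extensive-versus-poor contrasts. AT-10-versus-clopidogrel contrasts on aggregation: 0.

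**Step 3. Compare with PK.** Section 14.3 serves a secondary objective. It lists AT-10 against clopidogrel in extensive metabolizers and again in poor metabolizers, with ANOVA on log-transformed parameters, ratios of least-squares means and 90% confidence intervals. It also leaves room for further PK comparisons. Section 14.4 has neither the drug contrast nor such an allowance.

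**Step 4. What the missing contrast could deliver (illustration only).** Assume 20 completers per metabolizer type, a 2×2 crossover with 18 degrees of freedom, and a within-subject SD of 10, 15 or 20 percentage points of inhibition. The protocol gives no SD; this range is assumed.

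SE = SD × √(2/20) = 0.316 × SD. The 90% half-width is t(0.95, 18) × SE = 1.734 × 0.316 × SD = 0.548 × SD:

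- SD 10: 5.5 points
- SD 15: 8.2 points
- SD 20: 11.0 points

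**Step 5. What a formal equivalence test would face (illustration only).** Simulated power of two one-sided 5% tests, same assumptions, true difference zero:

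| Assumed margin (points) | SD 10 | SD 15 | SD 20 |
|---|---|---|---|
| 10 | 84% | 31% | 5% |
| 15 | >99% | 84% | 48% |
| 20 | >99% | 98% | 84% |

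**The case against.** The best reply is that a protocol may leave models, contrasts and margins to a SAP, and 14.4 does not call its contrast the only or the primary one. This stands in part. A reader might infer that AT-10 will never be tested against clopidogrel on aggregation; the documents do not support that, because a SAP may exist and could add the test. What remains is that the protocol is not silent: in two places it fixes a contrast that does not answer its own primary objectives.

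Second, results by treatment group at each time point would show both drugs in each metabolizer type, and objective 2 speaks of comparing, not testing. True, but this is description without a stated estimate of the difference or its uncertainty.

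Third, objective 3 may be loosely worded. Section 6.2 says the doses were already selected as pharmacodynamically similar in an earlier study in extensive metabolizers, and section 8 describes proof-of-concept data. This stands: a formal equivalence test is one way to honour the objective, not an obligation, and the absence of a margin or a power calculation is not itself the fault.

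Fourth, the genotype contrast is useful. The rationale in 6.2 is that AT-10 may depend less on CYP2C19 than clopidogrel does, and comparing genotypes within each drug bears on that. It deserves to stay, as a secondary analysis.

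A reader might also infer that equivalence in poor metabolizers would count as failure of AT-10. Section 6.2 makes that a natural thought, but the protocol states no such criterion. What can be said is that objective 3 does not say which metabolizer type it refers to.

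**Conclusion.** The concern holds as a mismatch between objectives and analysis within this protocol. Two of three primary objectives have no matching inferential analysis in 14.4 or the synopsis: 38 genotype contrasts are implied and no drug contrast on aggregation, while the drug contrast is written in full for secondary PK. This conclusion comes from the text alone and needs no assumed figure.

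The half-widths of 5.5, 8.2 and 11.0 points show only that the missing estimate is obtainable. They rest on assumed SDs and on 20 completers per metabolizer type, which is optimistic because dropouts are not replaced. The power table shows why a formal equivalence claim may be more than this sample size can carry; it does not show that the sample size is wrong for its stated purpose.

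The mismatch should be settled before any aggregation data are examined. The study is open label and the samples are analysed at the site, so a contrast, measure or time point chosen later could not be shown to be independent of the results.

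**What to change.** In 14.4 and the synopsis:

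1. Make the primary PD analysis AT-10 minus clopidogrel within each metabolizer type, from a crossover model with sequence, period, treatment and subject within sequence, plus the volunteer-group effect that 14.4 already names.
2. Choose one PD measure. Section 14.4 currently allows either residual impedance or percent inhibition.
3. Name one time point for the loading phase and one for the maintenance phase, since objective 3 concerns both and there are 19 to choose from.
4. Report the estimated differences with confidence intervals, and keep the extensive-versus-poor contrasts as secondary.
5. In objective 3 (section 6.1 and synopsis), replace *confirm* with *estimate* and state that it refers to extensive metabolizers, in whom the doses were matched. The alternative is for the sponsor to prespecify a justified margin and judge it by a 90% confidence interval.

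Items 1 to 4 change wording only and use samples already scheduled. Item 5 has a price: objective 3 becomes a weaker claim, or the sponsor commits to a margin with uncertain power, which could reopen the sample size.
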